3. STUDY ENDPOINTS

3.1. *Primary endpoint*

Due to the study design (proof of concept) the endpoint will be completion of data collection.

4. STUDY VARIABLES

4.1. *Standard variables*

Gender

Age

Ulcer location

Classification of Ulcer (Texas classification)

Ulcer duration

Previous history of foot ulcer

Previous foot ulcer at same site

Duration of diabetes

Weight

Height

5. STUDY DESIGN

5.1. *Study description*

Observational proof of concept study comparing the ability to redistribute forefoot pressure using a new foot offloading device compared to usual standard care.

The sample will be purposively selected taken from a local population of active diabetic foot ulcer patients. The measurements will be taken from patients wearing usual standard of care, sham shoe (closest to barefoot or baseline pressures) and the PulseFlow DF boot. The measurements from each patient will be collated to compute pti averages for the comparison.

5.2. *Study duration*

Approximately four months or time to complete required maximum sample size of 36 or ending 1st July whichever arrives first.

5.3. *Rationale for study design*

The issue of a novel boot should not influence clinical practice or further research until data is produced to support it.

6. SELECTION AND WITHDRAWAL OF SUBJECTS

6.1. *Target population*

Patients currently undergoing treatment in the local Diabetic Limb Salvage Service who have diabetic neuropathic related plantar forefoot ulceration.

6.2. *Estimated number of eligible participants*

For this exploratory study formal methods for estimating sample size are inappropriate. The rationale for the size should be based on feasibility and the basis that this study will be used to justify the sample size of future studies. Therefore the rule of thumb modelling over three factors being explored will provide a sample size of 12 in each group (Julious, 2005). Therefore 36 in total are required. From a 2015 audit, theoretically there was a population size of 231 which identified 23% eligible patients for this study. The current population at January 2017 totalled 326 therefore approximately 74 patients should be eligible for this study. From the scoping exercise in December 2016, six patients were approached regarding the study to review possible challenges to taking part. All

Protocol version 1

Evaluating plantar foot pressure in a novel diabetic offloading device

IRAS code 198005

six patients were satisfied with the proposal of taking part considering time required hospital location, travel arrangements and consenting. Therefore it is considered feasible to recruit the required sample of 36 participants (49% of available population following inclusion criteria).

6.3. *Eligibility criteria*

6.3.1. *Inclusion criteria*

- (a) Plantar forefoot diabetic foot ulcer
 - a. over the 1st, 2nd, 3rd, 4th or 5th metatarsal joints
- (b) Neuropathic or Neuro-Ischaemic classification foot ulcer (taken from the TEXAS classification system)
- (c) Orthotic intervention for offloading/usual standard
- (d) English speaking and reading
- (e) Palpable foot pulses and/or Ankle Brachial Pressure Indices of values 0.8 to 1.29.

6.3.2. *Exclusion criteria*

- (a) Being treated for or having an active Charcot Arthropathy
- (b) Ankle Brachial Pressure Indices of <0.8 and >1.29. Using a standardised reproducible instrument called the Huntleigh Dopplex Ability Unit (DA100PB).
- (c) Temporary, accommodating or footwear not designed to offload.
- (d) Clinically active Infection causing lower leg swelling
- (e) Purely ischaemic classification foot ulcer
- (f) Current active osteomyelitis
- (g) Patients with forefoot trans metatarsal or major amputations
- (h) Fractures of the foot
- (i) Due to alterations in gait, patients with diagnosed vascular dementia, Parkinson's, alcoholism or other major medically related gait alterations i.e. intoxication, brain cancers, muscular degeneration diseases, inflammatory arthritis, etc. This does not include osteoarthritis.
- (j) Pregnancy
- (k) Under another trial regarding foot dressings or off loading

6.4. *Withdrawal criteria*

Protocol version 1**Evaluating plantar foot pressure in a novel diabetic offloading device****IRAS code 198005**

If the participant wishes to withdraw from the study at any point they are free to do so. Information regarding this is on the patient information leaflet. If withdrawing consent from the study is after data collection the data and samples will remain on file and will be included in the final study analysis as this will be anonymised.

6.5. Recruitment, consent and randomisation processes

6.5.1. Recruitment

A verbal explanation of the trial and Patient Information Sheet will be provided by the authorised trial clinician in the patient's usual standard of care treatment for the patient to consider. This will include detailed information about the rationale, design and personal implications of the study. Following information provision, patients will have at least 48 hours to consider participation and will be given the opportunity to discuss the trial with their family and healthcare professionals before they are asked whether they would be willing to take part in the trial. This process will be clearly documented into the patient's medical notes.

6.5.2. Consent

Identifying patients within their out patient appointments will be by the direct care team members with a GCP trained certification. Certification will be documented within the study folder. Assenting patients will then be formally assessed for eligibility and invited to provide informed, written consent.

Due to time and financial constraints of this educational study, it will not be possible to accommodate the communication needs of participants where English is not their first language. The right of the participant to refuse consent without giving reasons will be respected. Further, they will remain free to withdraw from the study at any time up to 24hours following (participant) data collection without giving reasons and without prejudicing any further treatment. Immediately after data collection participation will be pseudo anonymised. A copy of the consent will be given to the patient, one filed in the Study Files, and one filed in the hospital notes. The written consent will be taken by the principal investigator. The process of obtaining written consent will be clearly documented in the patient's medical notes.

6.5.3. Randomisation process

Due to the type of study design patients can not be randomised. However the process of measuring usual standard of care, standard shoe and PulsFlow DF can be randomised. This will be performed by using a Latin 3x3 square design below which will be randomly allocated from a computer programme at the appointment time of measuring the foot pressures.

Protocol version 1**Evaluating plantar foot pressure in a novel diabetic offloading device****IRAS code 198005**

Sequence 1	Usual standard care	PulseFlow DF Boot	Standard shoe
Sequence 2	B PulseFlow DF Boot	Standard shoe	Usual standard care
Sequence 3	Standard shoe	Usual standard care	PulseFlow DF Boot

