6.6. General information on the products or interventions to be used

PulseFlow DF

The Diabetic Boot Company Ltd, Trading as PulseFlow Technologies, [name].

UK Patent GB 2454089 - Dec 2009

US Patent US 8,388,562 - Mar 2013

FDA Registered Facility - Registration Number: 3012177215, Owner Operator Number: 10051096

PulseFlow DF is indicated for the treatment of active diabetic foot ulcer at the following sites: Plantar aspect of the 1st metatarsophalangeal joint (MTPJ), 2nd - 5th MTPJ, Heel, Plantar and dorsum aspects of the toes and the Dorsum of the foot.

Protocol version 1

Evaluating plantar foot pressure in a novel diabetic offloading device

IRAS code 198005

Proof of concept and pilot studies using healthy and patients with diabetic foot ulcers were used without reporting any adverse reactions. Diabetic foot ulcer patients showed one loss to follow up and one excluded from a small nine patient study to healing. All seven out of the nine patients at study end healed within a six week period.

6.7. ***Use within the trial***

PulseFlow DF Boot

- The PulseFlow DF boot is a trainer design with an integrated ankle foot orthosis. This is made of a metal design to immobilise the ankle and house the battery component around the calf region which will not be in use but with the same weight. Training of application and use of the device will be provided by the company producing the offloading device (Pulseflow Technology).
- The principal investigator will administer and supply the device at the time of data capture. This will be applied and then a recommended period of use will be given before data capture.
- Once the principal investigator and patient are satisfied with the safe use of the device it will be re-applied with the pressure sensing insole inserted.
- There will be no implementation or continuation of the offloading device following completion of data collection. However, information of the device, where it can be purchased from and how much will be offered to the patient as they are currently available to the public and healthcare practitioners.

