7. METHODS OF ASSESSMENT

This will be lab based data collection via electronic software, a modified validated questionnaire and demographic/variable list of specific identifying features of diabetic foot ulcers.

7.1. ***Efficacy assessment variables***

1. Usual care (offloading) device name/description
2. PulseFlow DF
3. Standard shoe

7.2. ***Routine laboratory assessments***

Gait laboratory

Pressure Time Integral

One laboratory will be used within the Leeds Teaching Hospitals NHS Trust. The Gait laboratory is situated within Chapel Allerton Hospital, Leeds. The measurements will be collected on pressure in kPa via the Pedar-xf analyser (novel, no date) automatically collected within self contained password protected computer software package and then held on the secure server of University of Leeds M Drive. This will be stored electronically, password protected (see 8.3.2 for full details) under patient identifiable data (participant study code) for analysis later. The first one collected will be analysed for quality analysis in efficacy and validity issues. Only the research team ill have access to this data.

Questionnaire

A modified validated Measure of Orthopaedic Shoes (MOS) questionnaire will be completed following the pressure measurements. Answers will be recorded on coded patient specific sheet to be collected and uploaded onto a prepared excel data base after the participant has left the appointment.

Protocol version 1

Evaluating plantar foot pressure in a novel diabetic offloading device

IRAS code 198005

The first one collected will be checked for completion. The completed questionnaire documents will be scanned and stored electronically to improve and allow for quality assurance to the transfer of data. This questionnaire will be used for the description analysis of patient acceptability.

7.2.1.1. *Gait analysis details*

Patients will familiarise themselves with the lab with a walking tour taking approximately up to 10minutes with question and answer session on the process of measurement taking and a chance to ask any questions. Then the measurement phase of walk assessment will start approximately 10minutes into the visit. A further 30minutes (total of 40minutes) is allocated to acclimatisation of the novel walking boot before this is used for gathering the measurements.

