The combined average of 3 steps or the middle one third of the 30 feet walkway will be used for assessment of PTI. The patient will be blinded from when the time the measurements are taken when walking for the measurement. This will be done by walking with the patient and taking a measurement after the patient has become acclimatised on the measured walkway. Acclimatisation will be quantified by the patient being able to walk and talk without the need of balance assistance i.e. hand on the patient's waist. The middle third of the walk will be used to acquire the measurements of PTI (approximately 3 steps of the foot)

7.2.1.2. *Duration of gait analysis*

Approximately 60 minutes will be given per patient visit to allow for technical and practical issues within the gait measuring room. The process for taking the electronic data measurements is estimated to take between 10 and 15minutes for all three devices however the overall practical process will take longer. The participant will then be allowed to complete the short questionnaire needed for the secondary analysis. This will take no longer than an additional 10minutes.

General Safety

Those experiencing hypoglycaemia from their diabetes at time of measurements will need to be addressed for patient safety reasons. Hypoglycaemia is measured or determined by the patient or the symptoms related to hypoglycaemia i.e. shaking, unbalanced walking, speaking incoherently, slow/slurred speech, sweating, feeling hot, disorientated and measured low blood sugars via the patient's blood sugar machine. When any participant has a hypoglycaemic event or becomes unwell the proceedings will be stopped. Hypoglycaemic events are not considered to

Protocol version 1**Evaluating plantar foot pressure in a novel diabetic offloading device****IRAS code 198005**

be caused by the intervention. The researcher will then seek appropriate medical care. The use of the nursing out patient hospital setting where the gait lab is situated will be used as support to any first aid issues. More serious events will be referred as appropriate to the nearest emergency care services. Rearranging the appointment will be offered following recovery.

7.2.1.3. *Data capture*

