9.4. Planned analyses

All data will be explored to check for assumptions of normality and homogeneity of variance for each variable, and to assess which statistical tests i.e. parametric or non-parametric test will be more appropriate to explore the data. The assumption of normality will be assessed graphically by histogram, box-plots and confirmed by statistical testing of significance of skewness and kurtosis. The spread, homogeneity and type of data will determine the type of statistical test. The paired t Test is predicted to be the statistical test of choice following statistician advice. This may change due to abnormal distribution of data once collection is complete.

Gait data will be checked for corruption or incomplete results associated with data capture or software error and rectified where possible either at the point of data collection or data analysis.

Exploratory statistical analyses will be performed to identify any potential associations between gait kinematics, clinical data and patient-reported outcomes. We will also explore the data for unexpected findings, including influential outliers, multicollinearity, truncation and missing data.

The primary outcome (section 2.2) will then be compared for systematic differences between the usual standard care and the PulseFlow DF boot using statistical tests based on the assumptions tested previously.

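### A cheap improvement, not an error of validity: the three cyclic orders in 6.5.3 leave the preceding device unbalanced, and using all six orders would make a carry-over check usable

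*Combined protocol and SAP*

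**What the plan says.** Section 6.5.3 explains that patients cannot be randomised between devices, but that "the process of measuring usual standard of care, standard shoe and PulsFlow DF can be randomised". The method is given as "This will be performed by using a Latin 3x3 square design below which will be randomly allocated from a computer programme". Three orders are printed: usual care, boot, standard shoe; boot, standard shoe, usual care; standard shoe, usual care, boot. Neither blocking nor equal use of the orders is mentioned.

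Section 6.2 sets the size by a pilot rule: "rule of thumb modelling over three factors being explored will provide a sample size of 12 in each group", giving 36. Section 5.2 allows fewer, since the study runs for the "time to complete required maximum sample size of 36 or ending 1st July whichever arrives first".

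Section 9.4 compares usual care with the boot. "The paired t Test is predicted to be the statistical test of choice following statistician advice", subject to the distribution of the data. No period, order or carry-over term is named.

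On the interval between devices, section 6.7 says of the boot: "This will be applied and then a recommended period of use will be given before data capture". Section 7.2.1.1 says: "A further 30minutes (total of 40minutes) is allocated to acclimatisation of the novel walking boot before this is used for gathering the measurements". It adds a criterion that is not worded as boot-only: "Acclimatisation will be quantified by the patient being able to walk and talk without the need of balance assistance". No washout between devices is stated, and all three are measured in one visit.

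**The concern.** Three conditions measured in sequence at one visit raise the question whether walking in one device affects the pressure-time integral (PTI) recorded in the next. A design can guard against this by letting each device follow each other device equally often. The printed orders do not: the two conditions in the primary contrast never share a preceding device. If usual care and the standard shoe leave different after-effects, the difference enters the boot minus usual care comparison. The planned paired test cannot reveal it, and in the printed design a model that adjusts for it is very imprecise. The study is also meant to inform the size of later studies (6.2), so a usable check on order effects has value beyond this pilot.

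**Working it through.** **Inputs from the documents.** Three orders (6.5.3); 36 patients, reproduced as 3 × 12 = 36 (6.2); boot minus usual care by paired t test (9.4).

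**Assumptions.** Orders used equally. Additive first-order carry-over: λ_U, λ_B and λ_S are the after-effects of usual care, boot and standard shoe on the next measurement. σ is the within-patient residual SD of PTI. The documents give no value for any λ or for σ.

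**Step 1. Preceding device, 36 patients.**

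| Pair | Printed (12 per order) | Six orders (6 per order) |
|---|---|---|
| usual care → boot | 24 | 12 |
| standard shoe → boot | 0 | 12 |
| standard shoe → usual care | 24 | 12 |
| boot → usual care | 0 | 12 |
| boot → standard shoe | 24 | 12 |
| usual care → standard shoe | 0 | 12 |

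**Step 2. Bias of the paired difference.** The weight of each λ is the share of boot measurements that follow that device minus the share of usual-care measurements that follow it.

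- Printed: usual care 24/36 − 0 = 2/3; boot 0; standard shoe 0 − 24/36 = −2/3. Bias = (2/3)(λ_U − λ_S).
- Six orders: usual care 12/36 − 0 = 1/3; boot 0 − 12/36 = −1/3; standard shoe 12/36 − 12/36 = 0. Bias = (1/3)(λ_U − λ_B).

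If every λ lies between 0 and L, the largest bias is 0.67L printed and 0.33L with six orders. As a range for the printed orders, an after-effect difference of 0, 0.1, 0.25, 0.5 or 1.0σ gives a bias of 0, 0.07, 0.17, 0.33 or 0.67σ.

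**Step 3. Precision of the boot minus usual care contrast.** Least squares with patient, period and device, without and with first-order carry-over (fixed patient effects, 36 patients):

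| | Unadjusted variance | Adjusted variance | Ratio | Adjusted SE |
|---|---|---|---|---|
| Printed | 2/36 = 0.0556σ² | 0.2778σ² | 5.0 | 0.527σ |
| Six orders | 0.0556σ² | 0.0694σ² | 1.25 | 0.264σ |

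The unadjusted SE is 0.236σ in both. With random patient effects at an assumed intra-patient correlation of 0.5, 0.7 or 0.9, the printed ratio is 4.2, 4.6 or 4.9, and the six-order ratio is 1.24 to 1.25. If recruitment stopped at 24, the adjusted SEs would be 0.645σ and 0.323σ.

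**Step 4. After-effects that depend on the next device.** Suppose acclimatisation removes carry-over into the boot only. The paired bias is then −(2/3)λ_S with the printed orders and −(1/3)(λ_S + λ_B) with six. For λ between 0 and L, the worst case is 0.67L in both. With an equal λ elsewhere:

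- the paired difference is off by −0.667λ in both designs;
- the six-order carry-over model is off by −0.625λ;
- the printed design's adjusted estimate is unbiased, with variance 0.2778σ² against 0.0694σ². Its mean squared error is the lower of the two only when λ exceeds √[(0.2778 − 0.0694)/0.625²] = 0.73σ.

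**Step 5. Strength of the check itself.** The SE of a difference between two after-effects is 0.707σ printed and 0.354σ with six orders. Power at two-sided 5% (66 df) for a difference of 0.35, 0.5 or 1.0σ is 8%, 11% and 29% printed, and 16%, 29% and 80% with six orders.

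**Step 6. Equal use of the orders.** If allocation were simple random (an assumption), an exact 12/12/12 split of 36 has probability 2.3%. The largest and smallest orders would differ by 5 or more patients in about 65% of lists.

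**The case against.** No carry-over is shown. PTI is recorded over about three steps, after the patient can walk and talk unaided, and the boot gets a further timed 30 minutes. After-effects may be negligible, and then the printed square, a recognised design, is valid. This stands. The criterion concerns balance, however, and is not itself evidence that pressure no longer reflects the previous device.

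Six orders are not better in every case. The boot is the unfamiliar device, and in the printed orders usual care never directly follows it. Six orders put usual care straight after the boot in 12 of 36 patients and give the boot's after-effect a weight of 1/3. Bias rises whenever |λ_U − λ_B| exceeds 2|λ_U − λ_S|. This stands as a real trade-off.

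The sensitivity model can also reassure falsely. With no carry-over into the boot and equal after-effects elsewhere, it and the paired test would nearly agree (−0.625λ and −0.667λ) while both are wrong, whereas the printed design's adjusted estimate is unbiased but far less precise. This stands too.

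Unequal allocation could be cured by blocking the three existing orders. That is true; it is a separate gain, and the simple-random figures rest on an assumption. Finally, this is a small single-visit pilot, and power for a 0.5σ after-effect difference is only 29% even with six orders. That argues for a modest recommendation, not for leaving the list as it is when the change is so cheap.

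**Conclusion.** The point holds as a recommended, low-cost improvement. The main gain is a usable check: carry-over adjustment multiplies the variance by 1.25 instead of 5, and the unadjusted variance does not change. These ratios assume equal use of the orders and additive first-order carry-over.

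A reader might infer two stronger things that the documents do not support. One is that the planned comparison is biased: nothing shows an after-effect, and position is balanced if the orders are used equally. The other is that six orders simply halve the bias. The fall from 0.67L to 0.33L is a worst-case result, and it needs after-effects that do not depend on the next device. The timed acclimatisation is stated for the boot alone, which makes exactly that condition doubtful. If it removes carry-over into the boot, the worst case is 0.67L under either set of orders.

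**What to change.** In 6.5.3, use all six orders of the three conditions, allocated in randomly permuted blocks of six. That gives 6 patients per order at 36, and counts within one of each other if recruitment stops early, apart from withdrawn or unusable data.

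In 9.4, keep the paired boot minus usual care comparison as primary. Pre-specify, as a sensitivity analysis only, a within-patient model with patient, period, device and first-order carry-over. State that disagreement between the two will be reported as uncertainty about order effects and not used to choose between them, and that agreement will not be taken as proof that there are none.

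Cost: a new randomisation list and one additional model, with no added patients, visits or measurements. The sensitivity estimate has 25% more variance than the unadjusted one, and the exposure of the primary contrast to the boot's after-effect should be acknowledged in the text.

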Pressure is measured in a standard unit of kilopascals (kPa). This can be measured by either a static plate embedded in the floor that a person walks across or an in-shoe device. There are several devices to measure pressure including the Pedar-xf analyser (novel, no date). The important considerations for use of such instruments are reliability and repeatability. The Pedar-xf has shown good levels of repeatability and reliability from linear loading with low errors measuring the coefficient of reliability at less than 10% for 93.4% of the parameters tested (Putti et al., 2007). This is practically due to the fact no two steps are identical to produce a 100% repeatable result. There is also good repeatability of loading at high pressures, seen in diabetic foot ulcer patients, as previous studies use healthy individuals (Hurkmans et al., 2006). The in-shoe device uses pressure cells imbedded in an insole which is placed between the foot and the device being measured. The insoles are 1-2mm in thickness. The sensors imbedded in them can detect pressure in kPa. The Pedar-xf analyser being used in this study for example has 99 sensors imbedded in a single insole. Since the interest is measuring pressure between a foot and a new offloading diabetic boot the appropriate instrument would be an in-shoe device.

The Pedar-xf Analyser System

The Pedar-xf system allows dynamic plantar foot pressures to be collected in-shoe simultaneously in both feet. Once this has been achieved the software can be instructed to apply masks to parts of the foot (Putti et al., 2007). The masking helps measure specified regions of the foot (Lavery et al., 2003, Hughes et al., 1993) such as the first metatarsal phalangeal joint. This allows clinicians to identify specific areas targeting specific off loading treatments such as recurrent ulceration sites and explore potential changes to plantar pressures (Arts et al., 2012, Ledoux et al., 2013).

Generating Outcome Measurements

Since pressure can be measured, the outcomes can generate data on contact area (cm^2), area under the peak pressure time curve (pressure time integral or pti) and peak plantar pressure (ppp) known as the single highest pressure calculated in kPa. The parameter of pressure time integral is less significant than ppp in risk factors for ulceration i.e. preventing DFUs (Bus and Waaijman, 2013). However in reducing pressure over an ulcer site rather than reducing the risk of ulceration, the

Protocol version 1

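### Does the 30-minute boot acclimatisation undo the time balance of the Latin square and bias the boot versus usual care comparison?

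*Combined protocol and SAP*

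**What the plan says.** Section 6.5.3 sets three orders: usual care, boot, shoe (sequence 1); boot, shoe, usual care (sequence 2); shoe, usual care, boot (sequence 3). On allocation it says: "This will be performed by using a Latin 3x3 square design below which will be randomly allocated from a computer programme". The first cell of sequence 2 reads "B PulseFlow DF Boot"; the stray letter changes nothing.

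Section 7.2.1.1 describes a familiarisation tour of about 10 minutes and continues: "Then the measurement phase of walk assessment will start approximately 10minutes into the visit". The next sentence is: "A further 30minutes (total of 40minutes) is allocated to acclimatisation of the novel walking boot before this is used for gathering the measurements". Section 6.7 says of the boot: "This will be applied and then a recommended period of use will be given before data capture". It then has the boot re-applied with the sensing insole once the investigator and patient are satisfied that it is safe. Section 7.2.1.2 adds: "The process for taking the electronic data measurements is estimated to take between 10 and 15minutes for all three devices", within a visit of about 60 minutes.

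The outcome is described in section 1.2 as the "area under the peak pressure time curve (pressure time integral or pti"). For the analysis, section 9.4 says: "The paired t Test is predicted to be the statistical test of choice following statistician advice". It allows a different test only if the distribution of the data calls for one. No period, sequence or time-in-visit term is planned.

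**The concern.** Randomising the order is meant to make effects of time in the visit, such as fatigue or growing ease on the walkway, cancel out of boot minus usual care. A Latin square does this when the three measurement slots are evenly spaced, or at least spaced the same way in every sequence. Here one device alone carries a half-hour block. If that block travels with the boot, position (first, second, third) stays balanced but clock time does not: the boot is always measured after the half hour, and usual care only in sequence 2.

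Pressure-time integral depends on how long the foot is loaded, so it would respond to a change in walking speed, and the protocol sets no speed. The comparison at stake is the primary one in section 2.2. With these three sequences, the usual crossover model could not recover the effect afterwards.

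**Working it through.** **Inputs.** Measurement phase from about minute 10 and acclimatisation of A = 30 minutes (section 7.2.1.1); 10 to 15 minutes for three devices, so m = 3.3 to 5 minutes each (section 7.2.1.2); 36 patients (section 6.2). Equal numbers per sequence, 12 each, are assumed; the protocol does not state blocking.

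**The protocol's own figures.** 10 + 30 = 40 minutes, as stated. Adding 10 to 15 gives 50 to 55 minutes, inside the visit of about 60.

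**Placement 1: the half hour comes just before the boot (m = 5).**

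| Sequence | Usual care at | Boot at | Boot minus usual |
|---|---|---|---|
| 1 | 10 | 10 + 5 + 30 = 45 | 35 |
| 2 | 40 + 10 = 50 | 40 | -10 |
| 3 | 10 + 5 = 15 | 10 + 10 + 30 = 50 | 35 |
| Mean | 25 | 45 | 20 |

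In general the gaps are A + m, -2m and A + m, so the mean is 2A/3 whatever m is. That is 20 minutes at A = 30, 13.3 at A = 20 and 6.7 at A = 10. The shorter values matter because section 7.2.1.1 ends acclimatisation by a functional test of unaided walking and talking, not by the clock. With unblocked allocation of 36, the realised lag at A = 30 has a 95% range of about 13 to 26 minutes.

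Let g be the change in the outcome after the half hour. Usual care is before it and the boot after it in sequences 1 and 3; both are after it in sequence 2. The weight of g in boot minus usual care is (1 + 0 + 1)/3 = 2/3.

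**Can the analysis remove it?** The indicator for being measured after the half hour equals period (0, 1/3, 2/3) + device (usual 0, boot 2/3, shoe 1/3) + sequence (0, 1/3, -1/3). For example, usual care third in sequence 2 gives 2/3 + 0 + 1/3 = 1. The patient, period and device columns number 36 + 2 + 2 = 40; adding the indicator makes 41 columns of rank 40. It is fully aliased in that model. Separation needs stronger assumptions. With no period effects the variance doubles (from 2/36 = 0.0556 to 0.1111, in units of the within-patient variance). With random patient effects it is multiplied by 5, 9 or 14 at assumed intraclass correlations of 0.5, 0.7 or 0.8.

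**What it could do.** The documents give neither g nor the within-patient SD. If g is assumed to be 0.1, 0.3 or 0.5 SD, the bias is 0.07, 0.20 or 0.33 SD. Dividing by the standard error √(2/36) = 0.2357 gives z = 0.28, 0.85 and 1.41. The coverage of a 95% interval, Φ(1.96 - z) - Φ(-1.96 - z), is then about 94%, 86% and 71%. If g = 0 there is no bias.

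**Placement 2: the half hour comes before all three recordings.** The gaps are m, -2m and m; the mean is 0 and the weight on g is 0.

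**Which placement does the text describe?** Taken strictly, a first recording at minute 10 fits neither: in placement 2 nobody is recorded before minute 40, and in placement 1 sequence 2 is not either. If the measurement phase can open with acclimatisation, placement 2 fits all the timings: 40 minutes in total, then one run of 10 to 15 minutes for three devices. Removing and re-applying the boot (section 6.7) fits both placements. The content of the patient contact schematic is not visible in the text reviewed.

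**Would prescribing placement 2 be free?** Let cU, cB and cS be the after-effect of each device on the next recording, with none of the boot on itself. Under placement 1 the boot always follows its own acclimatisation, so boot minus usual care carries 0, -cS and -cS in the three sequences. The weights on (usual, boot, shoe) are (0, 0, -2/3). Under placement 2 the sequences carry cU - cB, -cS and cU - cS, with weights (+2/3, -1/3, -2/3). If an after-effect of the boot on itself is also counted as cB, the boot weight becomes 0, but the +2/3 on usual care remains.

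**The case for a change.** The best case for a change is that it is cheap and must be made before data collection. A few sentences in section 7.2.1.1 would fix one slot; the sample size, sequences and test would stay as they are; and the aliasing means that no later analysis can repair a lag once it is in the data. Adding the other three orders would not cure it either, since with all six the lag is still 15 minutes. If the up-front placement was always intended, the sentences would only confirm it.

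The arithmetic in this stands, and so does the observation that the visible text does not fix the placement. Two parts do not stand. First, the lag belongs to one reading, and the visible text does not favour that reading. Second, a fixed slot is not a pure gain: it exchanges an unknown drift over time for an unknown after-effect of usual care on the boot, with the same weight of 2/3. Putting a short standard-shoe walk after the slot would not avoid this, because the boot would still follow usual care in sequences 1 and 3. It would also mean extra steps for patients with active forefoot ulcers in the shoe that section 5.1 describes as nearest to barefoot.

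**Conclusion.** No change to the plan follows. The gap is one of operational detail: where a boot-only half hour sits in a single visit. The protocol has one investigator collect all the data (section 9.1) and rehearse the process on three non-study patients (section 6.7), so the running order will have to be settled in practice before the first participant. That makes consistent handling likely, though it does not guarantee the up-front slot.

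The possible size is a lag of 2A/3 minutes, 20 if the full half hour is used just before the boot with equal allocation, and 0 if it precedes all recordings. Any resulting bias is 2/3 of a drift whose size and direction the documents do not give, so the coverage figures above illustrate assumed values and are not findings about this study. Giving acclimatisation only to the boot is itself reasonable, since patients enter already using an orthotic offloading device as usual care. The conclusion rests on the visible text; a schematic or laboratory instruction that put the half hour immediately before the boot would make the 20-minute lag real, though still of unknown consequence.
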